## **Statistical Considerations**

### **Power and Sample Size**

In order to ensure that the RCT has adequate power to determine the efficacy of the SMART 2.0 intervention to improve weight in kg, we calculated the sample size based on a two-sided, two-sample t-test with 80% power at a significance level of 2.5% (a Bonferroni correction to account for two tests). In the SMART study, the standard deviation (SD) of change in weight at 6 and 12 months ranged from 3.87 kg to 5.97 kg, and we have assumed that the corresponding SD in SMART 2.0 will fall within this range. Furthermore, the smallest statistically significant mean difference in change in weight between the two groups occurred at 12 months and was approximately -1.33 kg. If we assume an SD of 4.92 and a modest increase in the between group difference (-1.60 kg), then we will need 182 subjects per group in order to detect a minimal standardized effect size of 0.33. Thus, we will randomize 642 participants (214 per group accounting for a 15% attrition rate).

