### **Overall Approach**

Analyses will be conducted using the latest version of the statistical software platform R and will be based on the intention-to-treat principle. All tests of significance will be two-sided and a p-value of 0.05 will be considered statistically significant. Summary statistics (e.g., mean, standard deviations, proportions) will be calculated for all variables of interest. Outliers will be assessed and variables whose distributions depart significantly from normality will be transformed. Appropriate non-parametric alternatives will be considered if parametric assumptions fail. No planned interim analyses for efficacy or futility will be conducted in this study.

- **Primary aim analysis:** The primary outcome of the study is change in objectively measured weight in kg, and the SMART 2.0 intervention groups will be compared to the control group using a mixed model of repeated measures (MMRM). The model will include change in weight from baseline at each post-baseline visit (i.e., 6, 12, 18, and 24 months) as the dependent variable. Fixed effects will include study group, visit, study group-by-visit interaction, weight at baseline, and any variables determined to be confounders. Visit will be treated as a categorical variable, and an unstructured variance-covariance structure will be used. Results will be reported as point estimates (mean differences between groups) and

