interval estimates (95% confidence intervals). An intervention effect will be concluded if the p-value for the study group-by-visit interaction contrast in the model at 24 months is statistically significant. Holm's method will be used to adjust the two p-values for multiple comparisons. This approach uses all available data and is robust to data missing at random (MAR). However, two additional approaches may be employed to examine the influence of missing data on the primary outcome analysis (which takes a likelihood-based approach to estimation, but does not directly impute data). First, we will model the probability of missingness as a function of baseline covariates and previous outcomes (using logistic regression). The inverse of the resulting probabilities will serve as propensity scores that will be included in the model of the primary outcome. If data are MAR or the probability of missingness can be fully explained by observable data, this approach produces asymptotically unbiased estimates. Second, in order to allow for the possibility that the MAR assumption may not hold (an assumption that is not empirically testable), we will use pattern mixture models in which the distribution of the primary outcome is assumed to follow a mixture of two distributions: one for those who complete follow-up and another for those who do not. These approaches will allow us to quantify the robustness of the study findings to missing data assumptions.

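### Holm is valid for the two primary contrasts, but step-down Dunnett gains a little power at the same 5% family-wise error; separately, the 95% intervals need a label, because they can disagree with the adjusted decision

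*Combined protocol and SAP*

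**What the plan says.** The combined protocol and SAP, section 8 (Overall Approach, primary aim analysis), fits an MMRM to weight change and compares each intervention arm with control. An effect is concluded from the p-value of the 24-month contrast, and Holm's "method will be used to adjust the two p-values for multiple comparisons". The general threshold is: "All tests of significance will be two-sided and a p-value of 0.05 will be considered statistically significant". Results are reported as mean differences with "interval estimates (95% confidence intervals"). The text neither calls these intervals unadjusted nor provides simultaneous ones.

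The Power and Sample Size text uses a "two-sided, two-sample t-test with 80% power at a significance level of 2.5% (a Bonferroni correction to account for two tests"). Section 10 (Recruitment) gives 1:1:1 allocation.

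**The concern.** There are two separate issues.

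**The test.** Holm works from the p-values alone and protects against any dependence between them. Here the dependence is known in advance: both contrasts subtract the same control mean. Ignoring this makes the first step slightly stricter than 5% family-wise error requires.

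**The intervals.** Holm requires the smaller p-value to be at most 0.025 before anything is declared, while an ordinary 95% interval excludes zero at p < 0.05. For a smaller p-value between those limits, the headline interval and the headline conclusion point in different directions. The plan does not tell the reader which governs the interpretation of the interval.

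**Working it through.** **Inputs.** From Power and Sample Size: SD 4.92 kg, difference 1.60 kg, 182 evaluable per arm, two-sided 2.5% per test, 80% power. From section 10: 1:1:1 allocation. From section 7, as smaller true effects: 0.79 kg (predecessor trial, 24 months) and 1.33 kg (its 12-month result).

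**The plan's own figure.** The standardised effect is 1.60/4.92 = 0.325. A two-sample t-test at two-sided 0.025 with 80% power needs 181.01 per arm, hence 182, which matches the plan. Attrition: 182/0.85 = 214.1, against 214 stated (214 × 0.85 = 181.9), and 3 × 214 = 642. The sample size reproduces apart from trivial rounding.

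**Correlation.** With equal arms and variances, each contrast has variance 2σ²/n, and the two share covariance σ²/n from the control mean. The correlation is (σ²/n)/(2σ²/n) = 0.5.

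**Critical values (normal).**
- Holm: step 1 at 2.241 (p ≤ 0.025), step 2 at 1.960 (p ≤ 0.05).
- Step-down Dunnett: step 1 at c, where P(|Z1| ≤ c and |Z2| ≤ c) = 0.95 with correlation 0.5. This gives c = 2.212 (p ≤ 0.0270). Step 2 is at 1.960.
- With 3 × 182 − 3 = 543 degrees of freedom, the first-step values are 2.248 and 2.218.

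Since 2.212 < 2.241 and the second step is the same, step-down Dunnett rejects whenever Holm does.

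**Where interval and decision disagree.** SE = 4.92 × √(2/182) = 0.516 kg. An ordinary 95% interval excludes zero beyond 1.960 × 0.516 = 1.01 kg. Holm's first step needs 2.241 × 0.516 = 1.16 kg, and Dunnett's needs 2.212 × 0.516 = 1.14 kg. So the disagreement arises when the larger observed difference is between 1.01 and 1.16 kg under Holm, or between 1.01 and 1.14 kg under step-down Dunnett. Once the first step is passed, the second contrast is tested at 0.05 and its ordinary 95% interval agrees with the test. At the ends of the plan's SD range (3.87 and 5.97 kg), the SE is 0.406 and 0.626 kg, and the Holm zone is 0.80 to 0.91 kg and 1.23 to 1.40 kg.

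**Simulation.** 2,000,000 draws of two z statistics with correlation 0.5 and means equal to true difference/0.516. All results are percentages of trials; H = Holm, D = step-down Dunnett.

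| True differences (kg) | At least one rejected, H → D | Both rejected, H → D | 95% interval excludes 0 but rule finds no effect, H → D | Single-step Dunnett interval includes 0 for a contrast D rejects |
|---|---|---|---|---|
| 0, 0 | 4.65 → 5.0 | 0.8 → 0.8 | 4.4 → 4.1 | 0.4 |
| 1.60, 0 | 81.5 → 82.3 | 3.5 → 3.6 | 7.2 → 6.3 | 1.8 |
| 1.60, 0.80 | 81.8 → 82.6 | 32.7 → 32.8 | 6.7 → 5.9 | 8.4 |
| 1.60, 1.60 | 91.7 → 92.2 | 78.5 → 78.7 | 3.8 → 3.3 | 8.0 |
| 1.33, 1.33 | 78.9 → 79.9 | 58.6 → 58.8 | 7.8 → 6.9 | 9.9 |
| 0.79, 0.79 | 36.5 → 37.8 | 17.2 → 17.4 | 12.0 → 10.8 | 5.5 |

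Power for the working arm when the other has no effect rises from 80.8% to 81.6%. Per-arm power when both have 1.60 kg rises from 85.1% to 85.4%. With both arms null, at least one ordinary 95% interval excludes zero in 9.1% of trials, so joint coverage is 90.9%.

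**Sample size.** At Dunnett's first-step level, the normal approximation gives 177 per arm against 180 at 0.025. This is not a reason to change the planned size.

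**The case against.** The strongest reply is that nothing is broken. The decision rests explicitly on the p-value, Holm controls family-wise error under any correlation, and intervals play no part in the rule. The power gain is small, and the trial is already sized at a "significance level of 2.5% (a Bonferroni correction to account for two tests"), which is conservative for a Holm analysis and does not contradict it. All of that stands. It limits the point to a small improvement and a clarification.

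Four stronger readings are tempting, and the documents do not support them:

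- *The primary type I error is inflated.* It is not. Holm rejects in 4.65% of trials with both arms null.
- *The plan breaks a promise of 95% confidence.* It promises no joint coverage, and each ordinary interval has its stated coverage. That the intervals are unadjusted is itself inferred from silence, though it is the natural reading when only p-values are said to be adjusted.
- *Step-down Dunnett cures the disagreement.* It is a test. Beside ordinary 95% intervals, about 90% of the disagreement remains (for example 4.4% falls only to 4.1%).
- *Simultaneous intervals cure it cleanly.* Single-step Dunnett intervals never exclude zero without a rejection, because any |z| above 2.212 passes step one. But they bring the reverse conflict, an interval that includes zero for a contrast rejected at step two. With both arms at the planned effect this occurs in about 8% of trials, more than the 3.8% being removed. The 97.5% intervals beside Holm do no better (9.0%).

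**Conclusion.** The point holds as a small improvement, with no error in the primary test. Step-down Dunnett is never less powerful than Holm here and keeps family-wise error at 5%. It adds about 0.2 to 1.2 percentage points of power, and as little as 0.1 for rejecting both contrasts when the effects are unequal.

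The interval issue is one of labelling. The ordinary 95% interval can exclude zero when the rule finds no effect, in about 4% to 12% of trials over the scenarios run, and the choice between Holm and Dunnett hardly matters to it.

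The figures assume 182 evaluable per arm, equal variances, approximate normality and correlation 0.5. Unequal attrition would move the correlation, and a different 24-month standard error would move the zone in kg. Step-down Dunnett relies on the joint distribution of the two estimates, which Holm does not need. At this sample size that is a mild requirement.

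**What to change.** Make two changes to the primary aim analysis text.

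1. Replace Holm with the step-down Dunnett test of the two 24-month contrasts, at two-sided family-wise 5%, using the correlation estimated by the MMRM.
2. State that the 95% intervals are unadjusted for multiplicity and that the adjusted p-values decide whether an effect is concluded. This sentence is needed even if Holm is kept.

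Simultaneous 95% Dunnett intervals are optional. If they are shown, say that they are about 13% wider (2.212/1.960 = 1.129), that the test remains decisive, and that such an interval will include zero for a contrast rejected at step two in about 8% of trials when both arms have the planned effect.

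The cost is one or two SAP sentences and a routine computation in R, the plan's software. Sample size, conduct and data collection do not change.

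### Minor: the optional missing-data check inverts the probability of being missing, but the unbiasedness it claims belongs to weighting by the inverse cumulative probability of being observed

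*Combined protocol and SAP*

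**What the plan says.** All of this is in section 8 of the combined protocol and SAP, under Statistical Considerations.

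- **Primary model (Overall Approach).** A mixed model for repeated measures (MMRM) takes "change in weight from baseline at each post-baseline visit (i.e., 6, 12, 18, and 24 months) as the dependent variable". The decision rests on one visit: "An intervention effect will be concluded if the p-value for the study group-by-visit interaction contrast in the model at 24 months is statistically significant". Both p-values are adjusted for multiplicity by the Holm procedure.
- **Status of the check.** After the MMRM, "two additional approaches may be employed to examine the influence of missing data on the primary outcome analysis".
- **The first of these approaches.** Three statements follow one another: "we will model the probability of missingness as a function of baseline covariates and previous outcomes (using logistic regression"); then "The inverse of the resulting probabilities will serve as propensity scores that will be included in the model of the primary outcome"; then "If data are MAR or the probability of missingness can be fully explained by observable data, this approach produces asymptotically unbiased estimates".
- **Purpose.** Of both approaches together: "These approaches will allow us to quantify the robustness of the study findings to missing data assumptions".
- **Expected loss (Power and Sample Size).** "we will randomize 642 participants (214 per group accounting for a 15% attrition rate").

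The plan does not say whether the score enters as a weight or as a covariate. It does not say whether probabilities are combined across visits, or how intermittent missed visits are treated. Study group is not named as a predictor of missingness.

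**The concern.** The probabilities being inverted can only be the missingness probabilities of the preceding sentence, and no other section redefines them. The property then claimed is that of inverse-probability weighting, which uses the probability of being observed. Completers who resemble dropouts should count for more, because they stand in for people who left. Dividing by the probability of being missing makes them count for less.

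At stake is the reading of a robustness check. Programmed literally, it can disagree with a sound MMRM even though MAR holds, or return a noisier estimate, and so suggest fragility that is not there. Correcting it after the data are seen would be a post hoc choice.

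**Working it through.** **1. The plan's own figures.** Inputs from Power and Sample Size: difference 1.60 kg, SD 4.92 kg, two-sided 2.5%, 80% power, 15% attrition. The standardized effect is 1.60/4.92 = 0.325. An exact two-sample t-test needs 181.01, rounded up to 182 per group. 182/0.85 = 214.1, and 3 × 214 = 642. These reproduce and are not in dispute.

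**2. What the two inverses do as weights.** Take one arm of 214 with 15% missing. Assume (not in the documents) two equal halves of 107 with P(missing) of 0.05 and 0.25, which average 0.15. Completers are 107 × 0.95 = 101.65 and 107 × 0.75 = 80.25. With weights w1 and w2 for the low- and high-dropout halves, the high-dropout share is

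80.25·w2 / (101.65·w1 + 80.25·w2)

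| Weight | w1, w2 | Share, 0.05/0.25 | Share, 0.10/0.20 |
|---|---|---|---|
| Truth | – | 50.0% | 50.0% |
| None (completers) | 1, 1 | 44.1% | 47.1% |
| 1/P(observed) | 1.05, 1.33 | 50.0% | 50.0% |
| 1/P(missing), as written | 20, 4 | 13.6% | 30.8% |

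The w1, w2 column is for the 0.05/0.25 split. For 0.10/0.20, completers are 96.3 and 85.6, and the written weights are 10 and 5. In both cases the written weight ends further from the truth than no weighting.

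**3. From shares to the group difference.** Let D be mean change in the high-dropout half minus that in the low-dropout half. The error in an arm mean is (share − 0.50) × D: with 0.05/0.25, −0.059·D for completers, 0 for 1/P(observed) and −0.364·D for 1/P(missing). If both arms have the same split, the error in the treated-minus-control difference is −0.364 × (D treated − D control). It is zero when D is equal in the arms and takes either sign otherwise. The documents give neither D.

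**4. Why cumulative.** A 24-month weight is seen after four chances to be lost. If 15% loss were spread evenly, the per-visit probability of staying would be 0.85^(1/4) = 0.960. A single-visit weight is then 1/0.960 = 1.04, while the cumulative weight is 1/0.85 = 1.18. In four-visit simulations (true difference −1.60 kg, SD 4.92, correlation 0.7, MAR dropout driven by the previous change, 600,000 per arm, four assumed dropout patterns), last-visit 1/P(observed) gave −1.51 to −2.00 kg. Cumulative 1/P(observed) gave −1.593 to −1.597 kg, and the unweighted MMRM about −1.60 kg.

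**5. How far the kg result moves with assumptions.** The dropout slopes and correlations here are assumed.

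- *Bias.* With 1/P(missing) as a visit-level weight and control/treated slopes of 0.20/0.05, 0.15/0.10 and 0.15/0.15 per kg, the large-sample difference was +1.41, −0.58 and −1.58 kg. When treated slopes were the steeper (treated/control 0.20/0.05, 0.30/0 and 0.30/−0.10), it was −4.18, −6.71 and −8.47 kg. These runs used logistic models with a group-by-previous-change term. With baseline weight and previous change only, the first two settings came back to about −1.4 and −1.5 kg.
- *Precision at 214 per arm.* With slopes 0.15/0.15, the SD of the estimate was 1.11 to 2.19 kg under the richer logistic model, 0.71 to 0.89 kg under the simpler one, and 0.51 kg for the MMRM. With slopes of 0 it was 0.98 to 2.11 kg, 0.52 to 0.55 kg and 0.49 kg.

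**6. The covariate reading.** With 1/P(missing) as a linear covariate, large-sample estimates ran from +0.07 to −2.17 kg. With 1/P(observed) as the covariate they ran from −0.24 to −2.34 kg. The truth was −1.60 kg. Swapping the probability does not cure this reading: the score is built from body weights recorded after randomisation, so adjusting for it distorts the group effect.

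**7. The outcome model matters too.** Correct cumulative weights, put as square-root observation weights into a correlated-errors MMRM, still gave −1.21 to −1.69 kg. The weighted 24-month comparison in step 4 did not have this bias.

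**The case against.** The strongest reply is that this is a slip of wording. The stated aim, unbiasedness under MAR, points any statistician to ordinary inverse-probability weighting. The check may never be run, and the primary analysis does not use the scores. All of that stands and is why the point is minor. It does not make the sentence executable: the literal instruction contradicts the property claimed for it, and the choice between weight and covariate is open.

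A second reply is that the inversion is not the fault if the score is a covariate, which is a natural reading of a propensity score included in a model. That also stands (step 6). The unbiasedness claim then fails for a different reason, and correcting the probability alone would not be enough.

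A reader might infer from steps 2 and 5 that the check will be wrong by some number of kilograms, or that it must lose several-fold precision. The documents support neither. They give no dropout pattern, and they name only baseline covariates and previous outcomes as predictors. Much of the larger precision loss comes from fitting a richer logistic model than the plan names.

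**Conclusion.** The point holds as a minor error in an optional analysis. As a weight, the inverse probability of missingness reverses the intended correction and lacks the claimed property. As a covariate, neither inverse has it in general.

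The shares in step 2 rest on the plan's 15% attrition and an assumed two-group split; the direction of the reversal does not depend on that split. In kg, the bias can be near nil or exceed 1 kg in either direction, and the precision loss runs from negligible to several-fold. No kg figure should be quoted as a property of the plan.

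A reader might also infer that the trial's conclusion is at risk. It is not: the MMRM is valid under MAR without these scores, and the Holm-adjusted 24-month decision and the sample size do not depend on them. The separate pattern-mixture approach is not touched either.

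**What to change.** Replace the sentences describing the logistic model and its inverse with:

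> We will model the probability of remaining observed at each visit, given study group (with a group-by-previous-weight term), baseline covariates and previous weights, among those observed up to the previous visit. Each observed record will be weighted by the inverse of the cumulative product of these probabilities up to that visit (stabilised if needed) in a weighted mean model for the primary outcome, with working independence and robust standard errors. Records after a first missed visit will be left out of this check only.

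Drop the term propensity scores. Working independence should be required rather than offered as an example (step 7), and the group terms let dropout depend differently on previous weight in each arm.

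The cost is wording only: same data and nearly the same logistic model. The check is less efficient than the MMRM, loses records after a first missed visit (these stay in the primary analysis), and remains a check under MAR. It says nothing about departures from MAR, which the pattern-mixture approach is there to address.
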